4.2 Analysis of the Clinical Utility Endpoints

Analysis of the clinical utility endpoints will be performed on the ITT population.

4.2.1 MDS-UPDRS

MDS-UPDRS will be administered at all scheduled visits 1-4.

The Total MDS-UPDRS and each of its components (Parts I through IV), and Parts II and III combined, as well as the changes from baseline in these scores, will be summarized by visit and treatment group, as well as for both treatment groups combined. Summary of study entry baseline of study IPX203-B16-02 will also be included.

4.2.2 PGI-S and CGI-S

The patients will rate the severity of their disease on a 7-point PGI-S scale ranging from “1: Normal, not at all ill” to “7: Extremely severely ill” at every visit.

Similarly, clinician’s global impression of severity will be rated on a 7-point CGI-S scale ranging from “1: Normal, not at all ill” to “7: Among the most extremely ill of subjects” at every visit.

PGI-S and CGI-S scores as well as their changes from baseline will be summarized descriptively by visit and treatment group, as well as for both treatment groups combined. Summary of study entry baseline of study IPX203-B16-02 will also be included.

Number and percentage of subjects with each score will also be summarized by visit and treatment group. Additionally number of subjects having PGI-S ≥ 4 , CGI-S ≥ 4 or PGI-S ≥ 5 , CGI-S ≥ 5 will be tabulated. Summary of study entry baseline of study IPX203-B16-02 will also be included.

4.2.3 PDQ-39 total score and individual domain scores

Parkinson's Disease Questionnaire-39 (PDQ-39) is a self-reported questionnaire. Using the 39 items, 8 domains are defined: mobility (Questions 1-10), activities of daily living (ADL) (Questions 11-16), emotional well-being (Questions 17-22), stigma (Questions 23-26), social support (Questions 27-29), cognition (Questions 30-33), communication (Questions 34-36) and bodily discomfort (Questions 37-39).

PDQ-39 will be administered at all scheduled visits 1-4.

Total scores will be calculated for the entire questionnaire and each domain. If at least one question is not answered then the total score and the affected domain score will not be calculated.

All scores and their changes from baseline will be summarized descriptively by visit and treatment group, as well as both treatment group combined. Summary of study entry baseline of study IPX203-B16-02 will also be included.

4.2.4 PAS total score and individual domains

Parkinson Anxiety Scale (PAS) is a 12-item patient or observer rated questionnaire with 3 domains: persistent anxiety (Questions A.1-A.5), episodic anxiety (Questions B.1-B.4) and avoidance anxiety (Questions C.1-C.3).

PAS will be administered at all scheduled visits 1-4.

Total scores will be calculated for the entire questionnaire and each domain. If at least one question is not answered then the total score and the affected domain score will not be calculated.

All scores and their changes from baseline will be summarized descriptively by visit and treatment group, as well as both treatment group combined. Summary of study entry baseline of study IPX203-B16-02 will also be included.

4.2.5 NMSS total score and individual domains

Non-Motor Symptom assessment scale for Parkinson's Disease (NMSS) is a 30-item investigator rated questionnaire. The NMSS contains 9 domains: cardiovascular (Questions 1, 2), sleep/fatigue (Questions 3-6), mood/cognition (Questions 7-12), perceptual problems (Questions 13-15), attention/memory (Questions 16-18), gastrointestinal (Questions 19-21), urinary (Questions 22-24), sexual function (Questions 25, 26), and miscellaneous (Questions 27-30).

NMSS will be administered at all scheduled visits 1-4.

Total scores will be calculated for the entire questionnaire and each domain. If at least one question is not answered then the total score and the affected domain score will not be calculated.

All scores and their changes from baseline will be summarized descriptively by visit and treatment group, as well as both treatment group combined. Summary of study entry baseline of study IPX203-B16-02 will also be included.

4.2.6 PDSS-2 total score and individual domains

Parkinson's Disease Sleep Scale-2 (PDSS-2) is 15-item self-reported questionnaire. Three

domains are defined: disturbed sleep (Questions 1-3, 8, 14), motor symptoms at night (Questions 4-6, 12, 13), PD symptoms at night (Questions 7, 9-11, 15).

PDSS-2 will be administered at all scheduled visits 1-4.

Total scores will be calculated for the entire questionnaire and each domain. Additionally sum of questions 9, 10, 11, 12, and 13 will be calculated. If at least one question is not answered then the total score and the affected domain score will not be calculated.

All scores and their changes from baseline will be summarized descriptively by visit and treatment group, as well as both treatment group combined. Summary of study entry baseline of study IPX203-B16-02 will also be included.

4.2.7 TSA

Treatment Satisfaction Assessment will be administered at visits 2-4. The subjects will rate their satisfaction with their PD treatment on a 7-point scale ranging from “1: Very much dissatisfied” to “7: Very much satisfied”.

TSA scores will be summarized descriptively by visit and treatment group, as well as for both treatment groups combined.

Number and percentage of subjects with each score will also be summarized by visit and treatment group. Also, the number and percentage of subjects with scores 5-7 (satisfied) vs. scores 1-4 (dissatisfied or neutral) will be tabulated.

4.2.8 ZBI-12

The 12-Item Zarit Burden Interview (ZBI-12) is used to assess the perceived burden of caregivers who provide assistance to patients with long-term progressive neurological disorders, including PD. The questionnaire consist of 12 questions, each answered on a scale from “0: Never” to “4: Nearly always”.

The ZBI-12 should be completed by the same caregiver during each scheduled visit.

Total score will be calculated by summing up the responses to all questions. If at least one question is not answered then the total score will not be calculated.

The total score and its change from baseline will be summarized descriptively by visit and treatment group, as well as for both treatment group combined.

Additionally the total score will be classified as follows:

- 0-10: no to mild burden
- >10-20: mild to moderate burden
- >20: high burden

Number and percentage of subjects at each category will be tabulated by visit and treatment group.

4.2.9 EMSQ

The EMSQ is a 3-question, subject-rated questionnaire that is used to assess whether a subject is experiencing any of 10 early morning PD symptoms by answering questions about prevalence

(Question 1), severity (Question 2), and response to the first morning dose of PD medications (Question 3). Study site staff will complete this questionnaire by questioning subjects during each scheduled visit.

For each symptom, number and percentage of subjects with each frequency and severity will be tabulated by visit and treatment group, as well as for both treatment groups combined. Whether the symptom improves after taking the first morning dose of the study drug will be similarly summarized. Summary of study entry baseline of study IPX203-B16-02 will also be included.

Total severity score will be calculated as the sum of severities across all 10 symptoms (None = 0, Mild = 1, Moderate = 2, Severe = 3). If the severity score is missing for at least one symptom, then the total severity score will not be calculated. The total severity score and its change from baseline will be summarized descriptively by visit and treatment group, as well as for both treatment group combined. Summary of study entry baseline of study IPX203-B16-02 will also be included.

5 SAFETY ANALYSES

Safety analyses will be performed on the Safety Analysis Set.

No imputation will be performed for missing safety data. In by-visit summaries, if a subject does not have a value collected at a given visit, this subject will not be summarized at that visit.

5.1 Adverse Events

Adverse Events will be coded using the Medical Dictionary of Regulatory Activities (MedDRA) version 22.0 AE coding system for purposes of summarization.

Only Treatment Emergent Adverse Events (TEAE) will be used for the summary analysis, unless otherwise specified. An AE will be considered as treatment-emergent if the date of onset is on or after the date of the first open-label study drug administration in the study IPX203-B16-03 and no later than 1 day after the last study drug dose in the study. AEs with unknown start dates will be counted as treatment-emergent unless the AE resolution date is prior to the first open-label study drug administration date. If the AE start date is partially missing, the AE will be considered treatment-emergent, unless the month and year (when available) rule out the possibility that the event occurred post start of the open-label study drug and no later than 1 day after the last study drug dose.

A TEAE is defined as treatment-related if it is recorded as “possibly related” or “related” to the study medication on the eCRF. AEs recorded as “not related” or “unlikely related” will be considered not related. In case the relatedness was not assessed, the most conservative result (related) will be chosen for the analysis.

In summaries of TEAEs a subject experiencing the same AE (with the same preferred term) multiple times will only be counted once for that preferred term. Similarly, if a subject experiences multiple AEs within the same system organ class, that subject will be counted only once in that system organ class. When summarizing AEs by severity, only the most severe occurrence within the preferred term or system organ class will be used. Similarly, when summarizing AEs by relationship to study drug, only the most related occurrence within the preferred term or system organ class will be selected for displays in summary tables.

An overall summary will include, by treatment group and overall, the number and percentage of subjects reporting at least 1 TEAE in the following categories:

- Any TEAE
- Treatment-related TEAE
- Serious TEAE
- TEAE leading to discontinuation of the study drug
- TEAE leading to death.

The following TEAE frequency tables will be prepared summarizing the overall number of TEAEs, the number and percentage of subjects reporting at least one TEAE by MedDRA System Organ Class (SOC) and preferred term (PT), by treatment group and overall:

- All TEAEs
- Serious TEAEs
- Treatment-related TEAEs
- AEs leading to discontinuation of the study medication
- TEAEs in subjects with COVID-19
- TEAEs by severity
- TEAEs by relationship to study drug.

TEAEs will also be presented by SOC, PT, treatment group and one of the following subgroups of AEs:

- Total daily dose on the day of AE onset, categorized as < 400, 400 to < 1000, 1000 to < 1400, 1400 to < 1800, 1800 to <= 2400, and >2400 mg
- Daily dosing frequency on the day of AE onset (2, 3, 4, etc. times a day)
- Time to first onset, defined as the study day of the first onset of AE of the given SOC or PT for the subject, categorized as <= 7 days, >7 to 30 days, >30 to 90 days, >90 to 180 days, and >180 days.
- Time period. In this analysis each AE will be assigned to all (possibly several) time periods as in the previous paragraph during which the AE was active (i.e. after onset and prior to resolution).

TEAEs will also be presented by SOC, PT, treatment group and one of the following subgroups of subjects:

- Age: < 65, ≥ 65 years old at Visit 1
- Sex: Males, Females
- Race: Caucasians, non-Caucasians
- Region: North America or Europe
- PD duration at Visit 1: <8 years or ≥8 years
- Concomitant medications: the following non-exclusive subgroups will be defined for subjects taking concomitant medications of the following categories:

- Amantadine
- selective MAOB inhibitors
- anticholinergic PD medications
- dopamine agonists
- others

Additional summaries of non-treatment-emergent AEs that started in the previous study IPX203-B16-02 will be provided:

- AEs that started in study IPX203-B16-02 and resolved in the current study vs. those that did not resolve, by SOC, PT and treatment at the onset of AE (IPX203 or IR CD-LD and both treatments together)
- AEs that started in study IPX203-B16-02 and ended in the current study vs. are ongoing at the end of the current study by SOC, PT and treatment at the onset of AE (IPX203 or IR CD-LD and both treatments together)

For this analysis AE will be defined as resolved if its outcome is recorded as “Recovered/Resolved” or “Recovered/Resolved with Sequelae” in the eCRF. All other AEs will be considered not resolved.

The summaries by SOC and PT will be ordered alphabetically by SOC and PT.

Additionally number and percentage of subjects with TEAE will be presented by preferred term only in the descending order of total frequency.

All information pertaining to adverse events noted during the study will be listed by subject, detailing verbatim, preferred term, system organ class, start date, stop date, severity, outcome, action taken and causal relationship to the study drug.

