12.2.2. Recording Adverse Events

Elicit information about AEs with nonselective questions such as: “Have you experienced any changes in your health status since your last visit?” Encourage subjects to report AEs at onset.

Record information for any AE that emerges from the time the subject signs the ICF until Study Exit.

Monitor each subject closely for the development of AEs and record all such events on the AE page of the CRF. Whenever possible, group signs and symptoms that constitutes a single diagnosis. For example, cough, rhinitis, and sneezing might be grouped as upper respiratory infection.

For each AE, record the onset date, severity, seriousness, relationship to study medication, date of resolution (or continuing), action taken, and outcome in the CRF. The Investigator is to make a causality assessment (relationship to study medication) for every AE.

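### SAP 5.1 defines TEAEs by onset date with no rule for worsening, so a feeder-study AE that worsens on open-label IPX203 falls outside the TEAE tables unless a new AE record happens to be opened

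*SAP*

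**What the plan says.** SAP 5.1 restricts the AE tables: "Only Treatment Emergent Adverse Events (TEAE) will be used for the summary analysis, unless otherwise specified". Both limits of treatment emergence are onset dates. The lower limit is "An AE will be considered as treatment-emergent if the date of onset is on or after the date of the first open-label study drug" (meaning its first dose in this study); the upper limit is "no later than 1 day after the last study drug dose in the study". Incomplete dates have their own default: "AEs with unknown start dates will be counted as treatment-emergent unless the AE resolution date is prior to" the first open-label dose, with a similar rule for partial dates.

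AEs that began in the feeder study are handled apart, and the SAP names their status: "Additional summaries of non-treatment-emergent AEs that started in the previous study IPX203-B16-02 will be provided". There are two such summaries. One covers "AEs that started in study IPX203-B16-02 and resolved in the current study vs. those that did not resolve"; the other covers "AEs that started in study IPX203-B16-02 and ended in the current study vs. are ongoing at the end of the current study". Both are split by SOC, PT and the treatment the subject was on when the AE began.

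On data collection, Protocol 12.2.2 says: "For each AE, record the onset date, severity, seriousness, relationship to study medication, date of resolution", followed by action taken and outcome. It asks for AEs that emerge between consent and study exit, and does not say what to do when an existing AE gets worse.

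**The concern.** Visit 1 is normally the same day as the last visit of IPX203-B16-02 (Protocol 6.1 and 8.1), so an AE can be ongoing when open-label dosing starts. The SAP expects this, since it plans two summaries for such AEs. Under an onset-only rule, whatever happens to that AE afterwards cannot make it treatment-emergent.

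The objective is long-term safety. Protocol 13.3 asks that subjects moved from IR CD-LD be examined for clinical improvement on IPX203; the AE tables have no matching view of an existing event that deteriorates after the move. The sponsor's own crossover study (Protocol section 4) gives reason to look: AEs were reported by 35.7% (10/28) during IPX203 and 7.4% (2/27) during IR CD-LD, and the five subjects with dyskinesia all had it during IPX203. An event such as dyskinesia can persist and change in grade, and its onset date says little about that.

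**Working it through.** The plan states no figure to reproduce. The check applies the SAP 5.1 rule to each type of carried-over AE, taking the first open-label dose as the day of Visit 1 (SAP 2.1).

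| Case | Treatment-emergent under SAP 5.1? | Where it is summarized |
|---|---|---|
| Began in B16-02, stopped by Visit 1 | No | Medical history (SAP 3.5) |
| Began in B16-02, ongoing, unchanged | No | The two carried-over summaries |
| Began in B16-02, ongoing, then more severe, serious or treatment-ending, same AE record | No, because the onset date does not move | The two carried-over summaries, by resolution or ongoing status only |
| Same, but the site opens a new AE record with a new onset date | Yes, if the new onset is within the window | TEAE tables; neither document asks for the new record |
| Start date unknown, or partial and compatible with the open-label period | Yes, by default, unless resolved before first dose | TEAE tables; a missing-date rule, not a worsening rule |
| Onset on the day of Visit 1 | Yes | TEAE tables |

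The third row is the gap. I looked for other places where the worsening would be counted:

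- **Carried-over summaries (SAP 5.1).** They show status at resolution or study end, with no severity, seriousness or discontinuation. Because they are split by treatment at onset, an AE that began on IR CD-LD and worsened on IPX203 is shown under IR CD-LD.
- **Time-period table (SAP 5.1).** It assigns AEs to every period in which they were active, but only TEAEs enter it.
- **Severity table (SAP 5.1).** It takes the worst occurrence within a preferred term, again among TEAEs only.
- **AE listing (SAP 5.1).** It includes severity and action taken, but gives no incidence, and seriousness is not among its named fields.
- **Summary over the whole IPX203 exposure (Protocol 13.6).** SAP section 7 postpones it to the Integrated Summary of Safety, so it does not help this report.

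Direction: the rule can only leave events out of the numerators and does not change the denominator (the Safety set). Against a definition that counts worsening, each affected rate is lower or equal. The any-TEAE rate moves least, because a subject with another TEAE is counted anyway; the preferred-term, serious and discontinuation rates have less of that protection.

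Size: subjects affected = N × (share with an ongoing AE at Visit 1) × (share of those whose AE worsens). The documents give N of approximately 300 and neither share, so the product cannot be computed.

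**The case against.** The strongest reply is that these events are not lost. Disposition is tabulated by primary reason (SAP 3.1), and an adverse event is one of the listed reasons (Protocol 7.3), so a subject who stops because a carried-over AE worsened can be counted there. SAEs up to 30 days after the last dose must be reported and entered on the AE page (Protocol 12.3.2). All AEs are listed. MDS-UPDRS Part IV, orthostatic hypotension, GCSI, NMSS and ECG are summarized by visit and prior treatment whatever the AE onset. The detailed discontinuation table in SAP 5.1 is labelled with AEs rather than TEAEs, although it stands in a list introduced as TEAE tables. Sites may also have eCRF instructions to open a new record on worsening; those are not among the documents, and the protocol's silence does not prove there are none.

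All of this stands as mitigation. None of it puts the event back into the TEAE incidence tables by rule.

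Three stronger readings are tempting and do not hold:

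- A reader might infer that the IR CD-LD group receives a new drug at Visit 1. Protocol 6.4 starts everyone on the regimen set in the IPX203 dose conversion period of B16-02, so for that group it is a re-exposure.
- A reader might infer that this group is half the population, or that many AEs are ongoing at rollover. The documents give neither the allocation or rollover split nor a count of carried-over AEs.
- A reader might infer that a worsened feeder-study AE can never be a TEAE. A new AE record or the missing-date default can make it one, though neither is designed to capture worsening.

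**Conclusion.** The concern holds for AEs with a known onset in IPX203-B16-02 that are ongoing at the first open-label dose and then worsen in severity, become serious or lead to discontinuation, where no new AE record is opened. They are excluded from the TEAE tables by the rule as written, and some will be displayed under a treatment the subject was no longer taking when they worsened. The TEAE, serious TEAE and discontinuation rates are biased downward.

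The size cannot be derived from the documents. A reader might put a number on it: assuming that 30-50% of 300 subjects carry an AE over and 5-15% of those worsen gives 300 × 0.30 × 0.05 = 4.5 to 300 × 0.50 × 0.15 = 22.5 subjects. Both shares are guesses with no support in either document, so that range is not an estimate. The finding about the rule does not depend on it. It does rest on the assumption that sites are not told elsewhere to record worsening as a new AE. The study is descriptive, so no test or error rate is affected.

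**What to change.** In SAP 5.1, extend the TEAE definition to include an AE ongoing at the first open-label dose that increases in severity, becomes serious, or leads to study-drug discontinuation on or after that dose and no later than 1 day after the last dose.

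In the carried-over summaries, add the number of AEs that became serious in B16-03 and the number that led to discontinuation. Seriousness and action taken are already AE fields (Protocol 12.2.2); the seriousness flag should be read against its value at the end of B16-02, so that an AE already serious there is not counted as newly serious. Add severity change where severity at Visit 1 and later is available, or where a new AE record marks the worsening. Where it is not available, state the limitation in the SAP and the report.

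The SAP is to be finalized before database lock (SAP section 1), so the definition can still be changed if lock has not occurred. The cost is slightly higher TEAE counts and some extra programming. Severity change will be captured incompletely for data already collected, because the protocol lists severity once per AE and names no date of change. The SAP already carries COVID-19 adaptations, so collection may be well advanced; a new recording instruction issued now would make recording uneven over time, and the report should say so if one is issued.

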12.3.2. Reporting Serious Adverse Events

Any SAE that occurs from the time the subject signs an ICF until 30 days after taking the final dose of study medication must be reported by the investigative staff to the Sponsor or the Sponsor's representative within 24 hours of knowledge of the event (see [Study Contact Information](#)).

An SAE form must be completed and sent to the Sponsor and/or the Sponsor's representative. All SAEs must also be recorded on the AE page of the CRF. Additionally, all SAEs must be reported to the institutional review board (IRB) per the IRB's requirements.

Those SAEs that are considered both serious and unexpected and related to the study drug are subject to expedited reporting. An "unexpected AE" is any AE where the nature or severity is not consistent with the current investigator brochure (IB) or if an IB is not required or available, the specificity or severity is not consistent with the provided risk information.

Unexpected fatal or life-threatening SAEs related to the study drug must be reported by the Sponsor to the appropriate regulatory authority in an expedited manner (ie, first report within 7 days of first knowledge by the Sponsor). The Sponsor will provide a final written report to that authority within 15 days of initial receipt of information on the event. The Sponsor or the Sponsor's representative will also inform all participating Investigators of the SAE.

Unexpected SAEs that are not fatal or life-threatening must be reported by the Sponsor to the appropriate regulatory authority as soon as possible but no later than 15 calendar days after first knowledge of the SAE by the Sponsor. The Sponsor or the Sponsor's representative also informs all participating Investigators of the SAE.

Subjects withdrawn from the study due to any SAE will be followed until the SAE is resolved or medically stable. Record all SAEs, regardless of severity and whether or not related to the study medication, on the appropriate page of the CRF.

The Investigator must determine whether the seriousness of the event warrants removal of the subject from the study. He/she should, in any case, institute appropriate diagnostic and therapeutic measures and keep the subject under observation for as long as is medically indicated, or refer the subject to appropriate health professionals.

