3. Samples for laboratory tests and ECG that were done outside of regular visits, due to COVID-19, will be included in the analysis and mapped to the closest protocol defined visit ([section 2.3](#)).
4. Subjects who discontinued for reasons related to COVID-19 pandemic will be summarized separately in the disposition tables ([section x](#))
5. Adverse events in subjects with COVID-19 will be summarized separately ([section 5.1](#))

6. Protocol deviations related to COVID-19 will be identified in the listing ([section 3.4](#))

7 Changes From Protocol-Specified Analyses

The protocol envisioned summarizing AEs, vital signs and ECG across the entire IPX203 exposure including information from the open-label extension and the prior IPX203-B16-02 study into which the subjects were enrolled. It was decided to postpone such analyses until an Integrated Summary of Safety (ISS) is prepared. Such analyses will not be done as part of this SAP.

Changes related to the COVID-19 pandemic are summarized in [section 6](#).

There are no other deviations from the protocol-specified safety analyses.

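### SAEs and deaths with onset 2 to 30 days after the last dose must be recorded on the CRF but enter no adverse event summary

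*SAP*

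**What the plan says.** Protocol 12.3.2 sets the SAE reporting period from consent "until 30 days after taking the final dose of study medication", and adds: "All SAEs must also be recorded on the AE page of the CRF". For AEs in general, Protocol 12.2.2 stops recording at Study Exit, so the SAE period is deliberately the longer one.

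SAP 5.1 starts from a general rule: "Only Treatment Emergent Adverse Events (TEAE) will be used for the summary analysis, unless otherwise specified". An event is treatment-emergent if it begins on or after the first open-label dose and "no later than 1 day after the last study drug dose in the study". The serious and fatal rows of the overall summary, and the table of serious events by system organ class and preferred term, are all defined on TEAEs.

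Three other statements bear on whether these events are counted elsewhere:

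- SAP 5.1: "Additional summaries of non-treatment-emergent AEs that started in the previous study IPX203-B16-02 will be provided".
- SAP section 6: "Adverse events in subjects with COVID-19 will be summarized separately", with a pointer back to section 5.1.
- SAP section 7, on pooling over the whole IPX203 exposure: "It was decided to postpone such analyses until an Integrated Summary of Safety (ISS) is prepared". The same section then declares that the SAP otherwise follows the protocol's safety analyses.

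The by-subject listing in SAP 5.1 is comprehensive: "All information pertaining to adverse events noted during the study will be listed by subject".

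**The concern.** The collection window and the summary window end 29 days apart, and nothing in the SAP bridges them. Long-term safety is part of the study's single objective. If the plan is followed as written, the SAE table and the death row can show fewer events than the CRF holds. A reader would have to recover the rest by hand from a listing whose named fields do not include seriousness.

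Part of the interval may be actively observed. Protocol 8.5 asks early withdrawals to complete the exit procedures, and Protocol 12.2.2 records AEs until Study Exit. If a subject stops the drug and attends the exit visit several days later, an SAE elicited there with onset after day 1 is left out of the counts even though site staff asked about it directly.

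The date rules also have an odd effect. An SAE with an unknown onset date counts as treatment-emergent unless it resolved before the first dose, whereas one firmly dated to day 2 does not. Better documentation removes an event from the count.

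**Working it through.** The plan gives no figure to reproduce here: the 300 subjects are an enrolment estimate, not a calculated sample size. The check has two parts.

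**1. Does any planned output count an SAE with a known onset on days 2 to 30?**

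| Output | Counts it? | Reason |
|---|---|---|
| Overall summary, serious and fatal rows (SAP 5.1) | No | TEAEs only |
| Serious events by SOC and PT (SAP 5.1) | No | TEAEs only |
| Non-treatment-emergent summaries (SAP 5.1) | No | Only AEs that began in IPX203-B16-02 |
| COVID-19 AE summary (SAP 6) | No | Refers to 5.1, where the table is of TEAEs |
| Integrated safety summary (SAP 7) | No | Outside this SAP; the deferral concerns pooled IPX203 exposure |
| Disposition (SAP 3.1; Protocol 7.3) | Partly | Shows a death that ends participation, not one after completion, and is not an SAE count |
| By-subject AE listing (SAP 5.1) | Listed only | No count |

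**2. How much of the collection period is left out?**

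Inputs: SAE collection to last dose + 30 days (Protocol 12.3.2); summary window to last dose + 1 day (SAP 5.1); visits at Months 3, 6 and 9 (Protocol, Table 2); about 300 subjects (Protocol 13.1). One month is taken as 365.25/12 = 30.44 days.

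- Gap: 30 − 1 = 29 days. Share of the post-dose window: 29/30 = 96.7%.
- Share of the period from first dose to 30 days after the last = 29/(treatment days + 30):
  - 9-month completer: 29/(273.9 + 30) = 29/303.9 = 9.5%
  - stop at Month 6: 29/(182.6 + 30) = 29/212.6 = 13.6%
  - stop at Month 3: 29/(91.3 + 30) = 29/121.3 = 23.9%
- Person-time for 300 subjects with full capture: 300 × 29/365.25 = 23.8 person-years. The counted window, if all 300 completed, is 300 × (273.9 + 1)/365.25 = 225.8 person-years.

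The documents give no SAE rate for this trial. As an illustration only, assumed rates of 0.02, 0.05, 0.10 and 0.20 SAEs per person-year, applied to 23.8 person-years with full capture, give about 0.5, 1.2, 2.4 and 4.8 uncounted SAEs. Capture will be lower than that, because no contact is scheduled after Visit 4 or early termination.

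**The case against.** The strongest reply is that Protocol 12.3.2 is a reporting rule. It governs notification and CRF entry and prescribes no table. The analysis text, Protocol 13.6, promises AE summaries for time in the extension and for total IPX203 exposure, and an event after Study Exit falls outside the first of these. The synopsis sentence on treatment-emergent AEs and SAEs can be read as limiting both. On that reading the SAP breaks no explicit commitment for post-exit events. **This stands in part.** No passage demands a 30-day SAE table. But the interval between last dose and Study Exit is time in the extension, and SAP section 7 discloses no restriction there.

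Second, the 1-day limit is pharmacologically reasonable: Protocol section 4 gives a levodopa half-life of 1.5 hours with carbidopa and reports no accumulation. **This stands, and the limit is not the complaint.** It supports a short window for on-treatment AEs; it does not explain why SAEs collected for a further 29 days are never totalled.

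Third, for a few passively reported events a listing may suffice, and percentages would rest on subjects who are not actively followed. **The ascertainment point stands** and has to be footnoted. The listing alone still gives no count by group.

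Fourth, the shares above measure calendar time, not lost information, and the event illustration rests on assumed rates with full follow-up. **This stands**, and the conclusion does not depend on the illustration.

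**Conclusion.** The concern holds and should be fixed. Fully dated SAEs and fatal events with onset on days 2 to 30 after the last dose must be recorded, yet they enter no AE or SAE summary. The gap is 29 of 30 post-dose days. Depending on when treatment stops, it is 9.5% to 23.9% of the SAE collection period in the cases worked above. The 23.8 person-years is what 300 subjects would contribute under full capture. SAP 1.3 allows enrolment above 300, while passive ascertainment pulls the real figure down. The number of events affected is unknown.

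The finding is limited to tabulation:

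- The events appear in the listing, and prompt reporting to the sponsor is unaffected.
- Events with an unknown onset date, or a partial one that month and year do not exclude, still count.
- An event that began by day 1 and later became serious or fatal is counted, provided the worsening keeps the original onset date. The documents do not say whether it does.

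The study is descriptive and no decision rule depends on these counts, so the consequence is an incomplete safety table, not a wrong test.

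**What to change.** Leave the TEAE definition as it is. Add to SAP 5.1 one summary, by treatment group and overall, of all SAEs and all deaths with onset from the first open-label dose through 30 days after the last dose. Split it into on-treatment (to last dose + 1 day) and follow-up (days 2 to 30), and footnote that events after study exit are passively ascertained and may be incomplete. It would also help, as a clarification, to name seriousness among the fields of the AE listing.

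The cost is a paragraph of SAP text and one more table. No new data are needed, because the protocol already requires these events on the AE page. Reported SAE and death totals may rise slightly, and the follow-up column cannot be read as a complete incidence.
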